7.9.1 Deaths

The number of deaths will be reported with descriptive statistics by treatment group and relation to study treatment: before, during or after stopping. The number of deaths occurring after the end of official follow-up will be reported separately.

Kaplan-Meier curves will be used to describe survival in each treatment group up to:

1. Completion of the End of Study visit, or 25 days after last study treatment.
2. Completion of the Week 48 visit, or study discontinuation.

7.9.2 Adverse events

Adverse events (AEs) will be classified by system organ classes (SOC) and preferred terms (PTs) using the MedDRA dictionary version 23.0.

A treatment-emergent AE (TEAE) is defined as any event arising or worsening after the start of study drug administration until 25 days after the last study medication intake.

A summary of TEAEs and non-TEAEs will be presented, showing total numbers of events and subjects having events:

1. Fatal outcome
2. SAE status
3. Other significant AEs
4. AESI status
5. Causality
6. Severity

7. Actions taken

The number of TEAEs, and number and proportion (%) of subjects having TEAEs by SOC and PT will be given by treatment group. The number of events will also be broken down by:

1. Severity (mild, moderate, severe)
2. Causality (related, not related)
3. Timing with respect to starting treatment (disjoint union of: ≤ 2 weeks, ≤ 4 weeks, ≤ 8 weeks, ≤ 12 weeks, ≤ 24 weeks, ≤ 48 weeks)
4. Tertiles of OR-1896 concentration at the Week 4 visit (total of 4 groups: None, and others classified into Low, Medium, and High according to observed tertiles)
5. Dose change groups (see 7.4)

Incidence rates for first events adjusted for exposure time will also be reported. They are calculated by dividing the number of subjects ever experiencing the event while on treatment by the number of days subjects were exposed to the study treatment.

All serious adverse events (SAEs) and other significant AEs will be evaluated case by case. Narrative descriptions will be included in the study report for all AEs leading to death, other SAEs, AEs leading to study treatment withdrawal, and certain other significant AEs (OSAEs).

Groups of treatment emergent AEs of special interest (AESIs) are defined by Standardized MedDRA Queries (SMQs) where noted, and by in-house search categories (IHSCs) defined as lists of preferred terms, otherwise. Statistics for the following AESIs will be reported:

1. Decrease in red cell parameters
2. Drug related hepatic disorders - comprehensive search (SMQ)
3. Haemorrhages (SMQ)
4. Headache
5. Hypokalaemia (SMQ)
6. Hypotension
7. Increased heart rate
8. Ischaemic heart disease (SMQ)
9. Neurocognitive disorder
10. Palpitations
11. Suicide/self-injury (SMQ)
12. Supraventricular tachyarrhythmias (SMQ)
13. Ventricular tachyarrhythmias (SMQ)

See Appendix 10.2 for the queries used to create the groups. If an SMQ has both a broad and a narrow definition, the narrow search will be used.

In addition to standard AE reporting, detailed characteristics will be reported for AESIs:

1. SAE status
2. Need for concomitant medications
3. Severity
4. Changes in dosage
5. Outcome
6. Timing with respect to starting treatment

7. Duration of event
8. Safety subgroups (listed in 6.2.14)

Further, for AESIs, 95% confidence intervals (CIs) will be reported for incidence proportions and incidence rates, and risk ratios and incidence rate ratios (with 95% CIs) between the treatment groups will be estimated.

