5.3 Dosing

5.3.1 Selection and timing of doses

The subjects will be randomised centrally to receive either levosimendan or placebo. The daily dose of oral levosimendan will be 1-2 mg (see section 5.3.2). The subjects will take the study treatment in the morning and when the dose is increased to 1 mg b.i.d., the second dose will normally be taken 12 hours later. Alternatively the investigator may specify to take the 2nd daily dose 6 hours after the morning dose or when going to bed, according to the clinical needs of the subject. The prescribed time of the second dose will be recorded in the CRF and should be the same each day unless changed by the investigator. It is recommended to take the study treatment about 1 hour before food intake or on an empty stomach. The morning dose of study treatment will be administered at the study centre during the visit days.

The total duration of study treatments will be 48 weeks.

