6.5.1.2 Assessment of adverse events

All AEs must be elicited, documented and reported by the investigator to the sponsor from the time that a study subject signs the IC form until the end-of-study visit (14-25 days after the last study treatment administration).

SAEs and other significant AEs should be followed up until resolved or until the event is considered a chronic or stable outcome, or both.

An AE may be notified to the investigator by the study subject (or his/her caregiver) or observed by the investigator clinically, or be an adverse change in laboratory assessment results. The investigator will evaluate the subject's AEs at each visit by asking a standard question such as "Since you were last asked, have you felt unwell or different from the usual in any way?"

The investigator will assess and record the causality and severity of the AEs. Causality should be assessed in relation to the investigational medicinal product (see criteria for causality and severity below).

Causality criteria:

Related: The temporal relationship of the AE/SAE onset to the administration of the investigational medicinal product makes a causal relationship possible, and other drugs, therapeutic interventions or underlying conditions do not provide a sufficient explanation for the AE/SAE.

Not related: The temporal relationship of the AE/SAE onset to the administration of the investigational medicinal product makes a causal relationship unlikely, or other drugs, therapeutic interventions or underlying conditions provide a sufficient explanation for the AE/SAE.

Severity criteria:

Mild: Discomfort noticed, but it does not affect normal activity.

Moderate: Discomfort sufficient to reduce or affect normal daily activity.

Severe: Incapacitating with inability to work or perform normal daily activity.

From the time that a study subject candidate signs the IC form, newly appearing diagnosed diseases will be recorded on the AE CRF.

Investigators must report all AEs to the sponsor on a specific AE CRF irrespective of their assessment of the causal relationship of the investigational medicinal product to the event.

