7.4 Extent of exposure and treatment compliance

The total number of exposed subjects, the total duration of study treatment exposure (continuous, and categorized both separately and cumulatively at the thresholds of ≤ 4 , ≤ 8 , ≤ 12 , ≤ 24 , and ≤ 48 weeks), and dose levels (in milligrams), averaged over the course of the study as well as at each study visit, will be reported as measures of extent of exposure.

Dose changes will be described by reporting the subject counts in the following categories:

- 1) remained at 1 mg for the entire study (“never increased”)
- 2) uptitrated to 2 mg and remained for the rest of the study (“increased and remained”)
- 3) uptitrated to 2 mg and later downtitrated to 1 mg (“increased, then decreased”).

Dose changes will also be reported by acetylation status.

Treatment compliance will be described by reporting the number of dispensed and returned study treatment capsules at each study visit. The number of subjects with treatment interruptions longer than 7 days will be reported with descriptive statistics.

Both extent of exposure and treatment compliance will be tabulated with descriptive statistics.

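### The TEAE timing table gives raw event counts in onset bins of unequal length with no time at risk, and it has no bin after Week 48

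*SAP*

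**What the plan says.** SAP 7.9.2 gives TEAEs by system organ class and preferred term for each treatment group, then states: "The number of events will also be broken down by" five factors. The third is "Timing with respect to starting treatment (disjoint union of: ≤ 2 weeks, ≤ 4 weeks", continuing "≤ 8 weeks, ≤ 12 weeks, ≤ 24 weeks, ≤ 48 weeks". No number at risk or subject-time is attached to it. Timing since the start of treatment appears again in the list of characteristics for adverse events of special interest (AESIs), with no bins or denominator given there.

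The same section defines a TEAE as "any event arising or worsening after the start of study drug administration until 25 days after the last study medication intake". Its exposure-adjusted incidence rate for first events is obtained by "dividing the number of subjects ever experiencing the event while on treatment by the number of days subjects were exposed to the study treatment". That is one rate per event over the whole treatment period.

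Protocol 5.3.1 says: "The total duration of study treatments will be 48 weeks". Protocol Table 1 sets baseline at Day 1 and Visit 8 (Week 48) at Day 337 ± 5 days. Study treatment is given at the centre on visit days. Protocol 6.5.1.2 has AEs collected up to the end-of-study visit, 14-25 days after the last administration.

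SAP 7.4 reports exposure duration as a continuous variable and also "categorized both separately and cumulatively at the thresholds of" at most 4, 8, 12, 24 and 48 weeks.

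**The concern.** A table of onset timing is read for its pattern over time. When bins differ 12-fold in length and carry no time at risk, the counts mostly reflect bin length. An event with a flat hazard looks as if it builds up late. Fewer subjects remain at risk in later bins, and the table does not show how many. Long-term tolerability up to 48 weeks is a stated objective, so the late part of this table will be read.

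The second gap is one of coverage. The TEAE definition continues past the last dose, but the bins stop at Week 48. For anyone who completes treatment, events arising after the drug is stopped have no row. The timing table will then not add up to the TEAE total, and the SAP does not explain the difference. SAP 7.9.1 does cover this period for deaths: one of its two survival curves runs to the end-of-study visit or 25 days after the last treatment.

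**Working it through.** The plan states no figure on this point, so there is none to reproduce.

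**1. Bin lengths.** The cut points are 0, 2, 4, 8, 12, 24 and 48 weeks (SAP 7.9.2). Their differences are 2, 2, 4, 4, 12 and 24 weeks.

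**2. Expected counts at a constant rate.** The expected count in a bin from *a* to *b* is the rate times the subject-time in it, that is the integral of S(t) from *a* to *b*, where S(t) is the fraction still at risk. Without dropout, S(t) = 1. For a fraction *d* lost by Week 48, take exponential loss: h = −ln(1−d)/48, and subject-time per subject = (e^(−ha) − e^(−hb))/h.

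The 20% figure is the total dropout allowance in SAP section 5. Spreading it over 48 weeks is an assumption, so other values are shown.

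| Bin (weeks) | Length | Share, no dropout | Ratio to first bin, no dropout | Ratio, 20% dropout | Ratio, 40% dropout |
|---|---|---|---|---|---|
| 0-2 | 2 | 4.2% | 1 | 1 | 1 |
| >2-4 | 2 | 4.2% | 1 | 0.99 | 0.98 |
| >4-8 | 4 | 8.3% | 2 | 1.95 | 1.90 |
| >8-12 | 4 | 8.3% | 2 | 1.92 | 1.82 |
| >12-24 | 12 | 25% | 6 | 5.54 | 5.01 |
| >24-48 | 24 | 50% | 12 | 10.20 | 8.29 |

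For the last bin at 20%: h = 0.2231/48 = 0.00465. Subject-time is 20.31 weeks, against 1.99 in the first bin, and 20.31/1.99 = 10.2. At 10% dropout the ratio is 11.1 and at 30% it is 9.3. Linear instead of exponential loss gives 10.24 at 20%. Also counting the 25 days after stopping for those who discontinue gives 10.33.

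**3. Effect of a denominator.** Dividing each count by its own subject-time returns a ratio of 1.0 at a constant rate, whatever the dropout.

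**4. Time after the last bin.** Under the protocol's day count, Week 48 is Day 337, which is 336 days after Day 1. If the last dose is taken on the day of Visit 8, the TEAE window ends 25 days later:

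| Last dose | Window ends | Days past Day 337 | Share of TEAE window |
|---|---|---|---|
| Day 332 | Day 357 | 20 | 20/(331+25) = 5.6% |
| Day 337 | Day 362 | 25 | 25/(336+25) = 6.9% |
| Day 342 | Day 367 | 30 | 30/(341+25) = 8.2% |

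Routine collection stops at the end-of-study visit, which may come as early as 14 days after the last dose. For a last dose on Day 337, the part actually observed is therefore 14 to 25 days.

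**5. Exposure categories.** The top category in SAP 7.4 ends at 48 weeks = 336 days. A last dose on Days 338-342 gives more than 336 days under either day count. A last dose on Day 337 gives 337 days if the first day is counted and 336 if it is not. So 5 or 6 of the 11 days in the Visit 8 window lead to no category.

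**The case against.** The strongest reply is that this is a descriptive table with labelled bins and a placebo arm beside it. Bin length is the same in both arms, so it does not distort the contrast within a bin. That stands. Event counts under 2:1 allocation still need a denominator to be compared, and unequal dropout would affect late-bin counts. SAP 7.1 does report time to treatment discontinuation by arm.

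A reader might infer that early headache or heart-rate effects would be masked. The documents do not support that. The first two bins are both 2 weeks long and divide at the Week 2 dose step, so an early excess shows directly as bin 1 against bin 2. The third and fourth bins are also equal. The 12-fold figure compares only the last bin with the first. Adjacent bins differ at most 3-fold.

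A reader might also infer that late TEAEs are lost. They are not: they remain in the overall TEAE tables and are absent only from this breakdown. Post-dose events in subjects who stop early will generally fall in a bin.

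AE enquiry becomes less frequent after Week 12, but the standard question in Protocol 6.5.1.2 covers the whole interval since the last enquiry. Nothing shows that onset dates move between bins as a result.

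Other analyses help in part. SAP 7.9.2 plans exposure-adjusted rates, with rate ratios for AESIs, but none is specified by time bin. The first-event rate counts only on-treatment events. The categories in SAP 7.4 show roughly how many subjects remain exposed at most bin edges, but they have no 2-week cut and give no subject-time. The continuous exposure summary keeps durations above 48 weeks visible.

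**Conclusion.** The point holds as a minor one. Followed as written, the timing table shows a constant event rate as a 12-fold rise from first to last bin within an arm. The rise is about 10-fold if 20% dropout is spread over 48 weeks, and about 8-fold at 40%. The no-dropout figure follows from the cut points alone; the others rest on the assumed dropout.

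For each completer, about 25 days of the TEAE window (20 to 30 across the Visit 8 window, about 7%) have no bin, so the bins do not sum to the TEAE total. This assumes the last dose is taken at Visit 8 and uses the protocol's day count.

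The exposure categories miss completers whose last dose falls late in the Visit 8 window, or on Day 337 if the first day is counted. The documents do not say how visit dates will be spread, so a statement such as half of completers being unclassified would go beyond them.

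No test or decision rule is tied to this table.

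**What to change.** - **SAP 7.9.2, timing item, and the AESI timing item:** for each bin and arm, report subject-time at risk and events per 100 subject-weeks beside the count. Count subject-time over the same window as the events, from first dose to 25 days after the last intake or to the end of AE collection if that is earlier.
- **Same items:** add a bin for TEAEs after Week 48 up to 25 days after the last dose, so that the rows sum to the TEAE total.
- **SAP 7.4:** make the top exposure category open-ended, for example > 24 weeks, and state whether the first day is counted.

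The cost is SAP wording and a few extra columns and rows in planned tables. Dosing and AE dates are already needed for the planned exposure and TEAE summaries, so no new data are required.

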After oral administration in healthy subjects, the maximum concentration (C_{max}) of levosimendan (mean approx. 45 ng/ml) in plasma was seen at 1 hour after doses of 1 mg once a day or 1 mg twice a day (b.i.d.). However, the active metabolite (OR-1896) concentrations increase slowly and steady-state is achieved after 12-14 days with constant daily dosing. The mean C_{max} of OR-1896 after 14 days of dosing with daily levosimendan doses of 1 and 2 mg were 1.6 and 2.8 ng/ml, respectively. The elimination half-life ($t_{1/2}$) of levosimendan is about 1 hour and that of the active metabolites 60 hours in healthy subjects.

Before the first phase IIa study in ALS (LEVALS, 3119001), oral levosimendan has been studied in healthy subjects, in patients with HF and in a small number of patients with a recent history of ischemic stroke/transient ischemic attack (TIA).

In the 2 earlier dose-ranging studies in 90 patients with HF, 5 doses of oral levosimendan from 0.25 to 4 mg or placebo were administered 4 times daily for 2-4 weeks. Daily doses of 4-16 mg had beneficial haemodynamic effects, but daily doses of 8-16 mg were associated with increased (> 10 beats per minute [bpm]) heart rate (HR). Despite high plasma levels of the active metabolite OR-1896 (1.3 to 28.5 ng/ml in the different dose groups), no signs of acute tolerability problems were seen.

The largest study with oral levosimendan, the PERSIST study (Nieminen MS et al., 2008), was a placebo-controlled study in 307 patients with severe chronic heart failure (CHF). The studied levosimendan doses were 1 mg once a day or 1 mg b.i.d. and the duration of exposure was at least 180 days. The results were inconclusive; quality of life (QoL) improved and the number of worsening HF events decreased, but mortality was numerically higher in levosimendan treated patients. The low overall mortality and the fact that the highest number of deaths was seen in the levosimendan 1 mg dose group with the most severe HF at baseline suggests that chance may have played an important role in distribution of deaths. HR increased by approximately 8 bpm compared to placebo in both levosimendan groups. In this study, HR increase and palpitations were the only adverse events (AEs) reported statistically more frequently with levosimendan compared to placebo. The numbers of atrial fibrillations or ventricular arrhythmias reported were similar between patients receiving levosimendan and placebo.

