5.3.2 Dose adjustment

The daily doses of oral levosimendan will be 1-2 mg depending on the tolerability (mainly judged by HR). The subjects will start with a 1 mg dose (in the morning) for 2 weeks.

HR will be assessed in the morning before study drug intake:

- At visit 2 (2 weeks):
 - If the HR in the 12-lead ECG has increased ≤ 15 bpm from baseline, the subject will increase the dose to 1 mg b.i.d.
 - If the HR in the 12-lead ECG has increased > 15 bpm from mean baseline value, the subject will continue with the 1 mg once daily. If the increase in HR is > 30 bpm in 3 separate recordings, the subject must discontinue the study treatment (see section 4.5).

- At visit 3 (4 weeks) or later visits:
 - If the HR in the 12-lead ECG has increased ≤ 20 bpm from baseline, no changes to the dosing regimen are made.
 - If the HR in the 12-lead ECG has increased > 20 bpm from baseline in 3 separate recordings taken within 5-10 minutes from each other, the subject will decrease the dose back to 1 mg once daily if treated with 1 mg b.i.d. In case the increase in HR is > 30 bpm in each of the 3 separate ECG recordings, the HR must be checked again at an additional visit approximately 2 weeks after the dose decrease. If the increase > 30 bpm is recorded at the dose level of 1 mg once daily in 3 separate recordings, the subject must discontinue the study treatment (see section 4.5).

Administration of placebo (1 or 2 capsules per day) will be based on the same criteria as described for levosimendan above.

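### Adverse events counted from the first dose are grouped by Week 4 OR-1896 tertile, although the Week 2 heart-rate rule helps to set that tertile; for heart-rate events the table could flatten or reverse the exposure-response

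*SAP*

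**What the plan says.** - **Event window.** SAP 7.9.2 defines a treatment-emergent event as one "arising or worsening after the start of study drug administration until 25 days after the last study medication intake". Neither that section nor the list of changes in SAP 7.11 sets a later start for any breakdown.
- **Grouping.** Item 4 of the breakdowns uses "Tertiles of OR-1896 concentration at the Week 4 visit". The table has four columns: one called *None*, and three more cut at the tertiles seen in the data. It does not say who belongs to *None*.
- **Dose rule in between.** Protocol 5.3.2 states: "The subjects will start with a 1 mg dose (in the morning) for 2 weeks". At Week 2 a rise of at most 15 bpm leads to the increase to 1 mg twice daily. If heart rate has "increased > 15 bpm from mean baseline value, the subject will continue with the 1 mg once daily". A third rule reads "If the increase in HR is > 30 bpm in 3 separate recordings, the subject must discontinue the study treatment".
- **Exposure by dose.** Protocol 1.1 reports that mean peak OR-1896 levels after 14 days on "daily levosimendan doses of 1 and 2 mg were 1.6 and 2.8 ng/ml, respectively".
- **Samples.** Protocol 6.3.1 takes the first concentration samples at Week 2 and the next at Week 4.

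**The concern.** An exposure-response table is read from left to right: if events become more frequent from Low to High, the drug is suspected. That reading needs exposure to come before the event, or at least not to depend on it. Here a subject whose heart rate rises early may have an event recorded in the first two weeks, be kept on 1 mg because of the same rise, and so have a lower concentration at Week 4. The early event is then counted under Low.

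The events concerned matter. Protocol 1.3.2 names increased heart rate and palpitations as the safety signals for the oral drug, SAP 7.9.2 lists both as events of special interest, and protocol 1.2.2 says heart rate rises with dose. A flat or falling row in this table could be taken as evidence against a concentration effect when it is a product of the titration rule.

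A second gap needs no calculation. A levosimendan subject stopped at Week 2 has no Week 4 tertile: after stopping, protocol 4.5 asks only for ALSFRS-R, ventilatory support and survival at the scheduled visits. The SAP does not say whether such a subject's events are dropped, shown apart or placed in *None* beside placebo.

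**Working it through.** The plan gives no figure for this table, so there is nothing to reproduce. Two checks were made.

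**1. Do Week 4 levels separate by dose?** The half-life is 60 h = 2.5 days (protocol 1.1, healthy subjects). The fraction of steady state after *d* days is 1 − 0.5^(d/2.5).

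- Day 12: 1 − 0.5^4.8 = 96.4%. Day 14: 1 − 0.5^5.6 = 97.9%. Both fit the 12–14 days stated in protocol 1.1.
- Dose raised at Week 2, level at Week 4: 1.6 + (2.8 − 1.6) × 0.979 = 2.78 ng/ml on average.
- Held at 1 mg: 1.6 ng/ml. The ratio is 2.775/1.6 = 1.73, close to the steady-state 2.8/1.6 = 1.75.

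So two weeks on the new dose are enough for the Week 2 decision to sort subjects by Week 4 level.

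**2. How strongly does this distort the table?** Simulation with 600,000 subjects per scenario, applying the Week 2 rules, with heart rate truly rising with OR-1896.

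Assumed, not in the documents:
- Between-subject CV of OR-1896: 30, 50 or 70%. Within-subject CV: 15%.
- Mean heart-rate rise at 1 mg and SD: (3, 8), (6, 8), (6, 10) or (8, 10) bpm. For the means, protocol 1.1 reports 6–8 bpm at 0.5–2 mg daily in one study and about 8 bpm over placebo in another.
- Chance of an early heart-rate event: 60% if the Week 2 rise exceeds 15 bpm, otherwise 3%.
- Chance of a later event: 60% if the Week 4 rise exceeds 20 bpm, otherwise 3%.

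This gives 3 × 4 = 12 scenarios, with 7–26% of subjects held at 1 mg. For 6 bpm, SD 8, the share of held subjects in Low/Medium/High is about:
- CV 30%: 31/8/2%
- CV 50%: 21/13/9%
- CV 70%: 15/14/15%

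With about 300 levosimendan subjects, a tertile holds about 100, so the CV 50% case means roughly 21 held subjects in Low against 9 in High.

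Percentage of subjects with a heart-rate event, Low/Medium/High (6 bpm, SD 8):

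| | CV 50% | CV 70% |
|---|---|---|
| Early events by Week 4 tertile | 15.1/10.2/8.0 | 11.8/10.9/11.5 |
| Early events by Week 2 tertile | 7.2/9.6/17.1 | 6.5/9.1/19.8 |
| Later events by Week 4 tertile | 5.7/7.3/15.7 | 5.0/6.7/17.9 |
| All events by Week 4 tertile (as planned) | 19.3/16.1/22.0 | 15.7/16.2/26.5 |

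Over the 12 scenarios:
- Early events by Week 4 tertile: Low above High in all 12. The smallest gap is essentially nil (the CV 70% column).
- Early events by Week 2 tertile: rising, the true direction, in all 12.
- Planned table: Low above High in 6 of 12. These are all 4 at CV 30% (for example 24.9/13.5/16.0%), 2 of 4 at CV 50% (for example 25.5/19.3/22.9% at 6 bpm, SD 10) and none of 4 at CV 70%.
- Later events by Week 4 tertile: High above Low in all 12, but not always in order (10.2/9.0/13.8% at CV 30%, 6 bpm, SD 10). Starting the count at Week 4 does not by itself remove the selection.

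**The case against.** **Other analyses cover much of this.** Item 3 of the same list breaks events down by time since start, including the first 2 and 4 weeks, and item 5 by dose-change group. SAP 6.2.14 summarises events by heart-rate-related dose changes. Events of special interest are compared between the randomised groups with risk ratios. SAP 7.9.4 plots post-dose heart rate against OR-1896 visit by visit, and SAP 3.2.2 foresees a PK/PD model that includes heart rate. This stands: the main safety signals do not depend on item 4, which is descriptive and carries no test. But items 3 and 5 are separate breakdowns, not crossed with tertile, and the plots show ECG heart rate rather than reported events such as palpitations.

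**The distortion may be small.** If OR-1896 raises heart rate, those held at 1 mg tend to form more of the metabolite, which moves them back up the tertiles. Protocol 1.1 gives a reason for wide spread: rapid acetylators form more OR-1896 than slow ones. This also stands, and is why the held subjects are spread almost evenly at CV 70%. A reader might infer a much stronger split by taking 15% held independently of their own exposure: that gives 32–40% of Low and 1–3% of High at CV 30–50%. It leaves out the exposure-response on which the concern itself rests.

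**The trigger is the ECG, not the event report.** Correct. The link holds only where the heart-rate rise, or a symptom going with it, is also recorded as an adverse event.

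**Conclusion.** The time-order fault is real and follows from the text: events count from the first dose, the tertile is fixed at Week 4, and a heart-rate rule sets the dose in between. For heart-rate-related events, item 4 could flatten or reverse the exposure-response. The importance is minor, because the table is descriptive and other analyses address the same signals.

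The size rests on the assumed spread of OR-1896, heart-rate response and event probabilities. Six reversals in 12 chosen scenarios show that the table is vulnerable; they are not a probability.

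Two stronger readings are not supported. A reader might infer that the table *will* assign heart-rate events to low exposure, but at CV 70% no scenario reversed. A reader might also infer that events of early stoppers *will* appear beside placebo. The SAP does not say so, and *None* can naturally be read as no exposure, that is, placebo. The fault there is a missing definition.

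**What to change.** In item 4 of SAP 7.9.2:

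1. Group events with onset before the Week 2 dose decision by Week 2 OR-1896 tertile. That sample is already collected, while all treated subjects are still on the starting dose.
2. Group events with onset on or after the Week 4 sample by Week 4 tertile, and show them also within dose-change group, because the later start alone leaves some selection.
3. Show events with onset between the two samples by treatment group only.
4. Restrict *None* to placebo, and give levosimendan subjects without a Week 4 sample their own column.

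The cost is onset filters, one more column and some extra tabulation, with fewer events per cell. No new data are needed and no dosing rule changes.
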